8.5.2 Other Data Analyses

Secondary analyses will include additional adjustment for factors showing possible imbalance at baseline and pre-planned exploratory analyses for differential effects of the intervention for different age groups, depression severity, and interaction (dose) of the Wysa app. Secondary analyses including adjustment for factors showing potential imbalance at baseline and pre-planned exploratory subgroup analyses for differential effects in a priori specified groups will be conducted using linear or logistic regression. For secondary analyses, where we have not specifically powered the study to detect statistical or clinical meaningful differences, we will report p-values but will focus on interpretation of 95% CI around estimates.

The qualitative semi-structured interviews will be evaluated using a thematic analysis.

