8.3.2 Sampling

8.3.2.1 Sample Size

Approx 1100 eligible patients are seen per month at the IAPT in the CNWL NHS Foundation Trust. Preliminary work suggests that Wysa is associated with a mean clinical improvement in PHQ-9 of 5.84 (SD6.66) [28]. This study is powered to detect a clinically meaningful effect on the PHQ-9 scale [28]. Based on a SD of 6.6 and a 2:1 recruitment ratio (usual care: intervention) a sample size of 393 would allow detection of a difference in PHQ-9 of at least 2 points, with 80% power. Augmenting the sample size to 480 would allow for 20% attrition, whilst still maintaining sufficient power to detect clinically and statistically meaningful differences with a Type 1 error rate of 0.05. This inflated sample size would also allow for adjustment for stratification variables, gender, age, ethnicity, self-reported antidepressant use, and severity of depression.

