8.4 Data Collection

8.4.1 Randomisation

8.4.1.1 Sequence Generation

Demographic data will be collected from all patients immediately after they complete the informed consent process, during the same phone call. Together with data from the IAPT referral, this information will be used in the randomisation algorithm to ensure that the intervention and control groups are balanced on key variables (gender, age, ethnicity, self-reported antidepressant use, and severity of depression).

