8.5 Data Analysis

8.5.1 Statistical Methods for Primary Outcome

Descriptive statistics will be used to characterise users, assess baseline comparability, and compare side effects. Primary comparisons between intervention and control groups will be conducted for primary and secondary outcomes. Primary analyses are designed with 80% power to detect a two-sided α of 0.05. All analyses will report 95% CI around estimate of effect. Comparative analyses will be conducted on an intention to treat basis, using linear or logistic regression, with adjustment for stratification variables.

We will explore missingness in our data, be that in relation to primary outcomes, follow-up data and in WYSA analytic information. The proportion of missing data will be explored and reported on descriptively. An hypothesised scenario, where patients remove themselves from the waiting list for treatment before the duration of follow-up may lead to missing data scenario. Currently, estimates

suggest that xxx% of our cohort will 'drop-off' waiting list before our primary endpoint. We will conduct exploratory sensitivity analyses in a complete case ('per protocol') cohort compared with the ITT analysis.

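### Extra covariates in the secondary models are chosen by observed baseline imbalance, so the baseline GAD-7, EQ-5D-5L and SF-12 scores enter their own models only by chance

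*Protocol*

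**What the plan says.** Protocol section 8.5.1 sets the main model. It states that "Primary comparisons between intervention and control groups will be conducted for primary and secondary outcomes", on an intention-to-treat basis, "using linear or logistic regression, with adjustment for stratification variables". Sections 8.3.2.1 and 8.4.1.1 give the factors as "gender, age, ethnicity, self-reported antidepressant use, and severity of depression".

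Section 8.5.2 then adds to that model. Secondary analyses are to include "adjustment for factors showing possible imbalance at baseline", and a later sentence in the same paragraph gives linear or logistic regression as the method for "adjustment for factors showing potential imbalance at baseline". The two sentences describe one analysis. Neither says which factors are candidates, how imbalance is judged, or how large it must be.

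The SAP specifies linear regression for PHQ-9 and GAD-7 and names no covariates, so it does not replace the imbalance rule with a fixed list. Section 8.4.3.1 has all participants complete PHQ-9, GAD-7, EQ-5D-5L and SF-12 at baseline and at 3 months.

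**The concern.** In a randomised trial a baseline difference between arms is a chance event. Adjustment gains precision from a covariate's relation to the outcome, not from how unequal the arms look. A rule based on imbalance leaves out a strong predictor that happens to be balanced and adds a weak one that happens not to be.

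The fixed set contains severity of depression but not baseline GAD-7, EQ-5D-5L or SF-12. Each outcome's own baseline score is usually its best single predictor, yet under section 8.5.2 it would enter that outcome's model only if it looked imbalanced. At stake is precision on three secondary outcomes. In addition, because the criterion is undefined, the content of the secondary models is settled only after the arms have been compared at baseline.

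**Working it through.** **Inputs from the documents.** Difference 2 points, SD 6.6 (6.66 is also quoted), 2:1 allocation, two-sided 0.05, 80% power, 393 evaluable (sections 8.3.2.1 and 8.5.1).

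**Assumptions.** The documents give neither a covariate-outcome correlation nor an imbalance threshold. I take r = 0.3, 0.5 or 0.6 for one extra baseline covariate, given the five factors already in the model, and a trigger of p<0.05 to p<0.20. They also give no SD or target difference for GAD-7, EQ-5D-5L or SF-12. The figures therefore describe an outcome on the PHQ-9 design scale, with 6.6 as the SD before the extra covariate enters.

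**1. The plan's own figure.** Smaller arm = (1 + 1/2) × (1.960 + 0.842)² × SD² / 2².
- SD 6.6: 1.5 × 7.849 × 43.56 / 4 = 128.2, so 129 and a total of 387.
- SD 6.66: 1.5 × 7.849 × 44.36 / 4 = 130.6, so 131 and a total of 393.

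The stated 393 reproduces. This point does not touch the sample size.

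**2. Power without the extra covariate.** With 131 against 262, SE = 6.6 × √(1/131 + 1/262) = 0.706. Power = Φ(2/0.706 − 1.960) = Φ(0.872) = 80.8%.

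**3. Power if it is always included.** The SD is multiplied by √(1 − r²), so the variance is multiplied by 1 − r².
- r = 0.3: variance × 0.91, SE 0.674, power 84%.
- r = 0.5: variance × 0.75, SE 0.612, power 90%.
- r = 0.6: variance × 0.64, SE 0.565, power 94%.

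**4. Power if it is included only when imbalanced.** This has no simple formula, so it was simulated. The variance factors come from runs with 128 against 256 (6,000 per setting), the power from runs with 131 against 262.

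| r | Variance factor, rule | Variance factor, always | Power, rule | Power, always |
|---|---|---|---|---|
| 0.3 | 0.94-0.98 | 0.91 | about 79-83% | 83-85% |
| 0.5 | 0.83-0.91 | 0.75 | about 82-83% | 90% |
| 0.6 | 0.77-0.91 | 0.64 | about 83-85% | 94-95% |

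The ranges span the triggers and include simulation error. The 79% at r = 0.3 lies below the 80.8% of step 2 for that reason; the rule's variance factor is never above 1.

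**5. How often chance triggers the rule.** With five independent candidate factors, the probability that at least one is flagged is 1 − (1 − α)⁵: 23% at p<0.05, 41% at p<0.10 and 67% at p<0.20.

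**6. Type I error (nominal 5%).**
- Rule applied mechanically: about 3-5%.
- Better of the base model and the mechanically triggered model: about 4.6-5.5%.
- Better of the models with and without the covariate, chosen freely after seeing results: about 6-8%.

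The excess in the last line comes from free choice between two models. It appears in the same way when no imbalance rule exists.

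**The case against.** The strongest reply is that the rule takes nothing away. Section 8.5.1 already adjusts the comparisons of primary and secondary outcomes for the five factors, and section 8.5.2 only adds to that. The likely main predictor of PHQ-9, severity of depression, is in the model whether balanced or not. This stands. A reader might infer that the PHQ-9 analysis forgoes this precision or has its model chosen after the fact; the documents do not support that. It also stands that the rule does no worse than the stratification-adjusted model alone. The loss is relative to naming the right covariates in advance, and deleting the imbalance wording would not by itself recover it.

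A reader might also infer that the rule inflates false positives to 7-8%. It does not, as step 6 shows. The only route to that figure is discretion exercised after results are known. Several features limit the route: imbalance is judged on baseline data, section 8.4.2 describes the evaluation team as blinded, and section 8.5.2 puts the emphasis on confidence intervals. They do not close it, because the criterion is undefined, p-values are still reported, and an interval from an unspecified model is just as open to choice. None of them restores precision.

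**Conclusion.** The point holds for the secondary analyses. Imbalance is the wrong selector, it has no stated criterion, and the baseline scores of GAD-7, EQ-5D-5L and SF-12 are left to it. For an outcome on the PHQ-9 design scale, the rule gives up about 7-8 percentage points of power at r = 0.5 and about 10 at r = 0.6, but only a few points at r = 0.3.

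The size depends on the assumed r, which is the correlation left after the five factors. Two things could push it down: severity of depression may already carry part of what baseline GAD-7 predicts, and the exclusion of scores above 15 narrows the baseline range. The primary PHQ-9 model, the sample size and the type I error of a mechanical rule are not in question. The protocol and SAP state the 2:1 ratio in opposite directions and must be reconciled, but with equal SDs this does not change the figures here. The change is worth making because it is nearly free; it is not a threat to the main result.

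**What to change.** For each outcome, name the covariates in advance: the five randomisation factors, with baseline PHQ-9 as a continuous score, plus the baseline value of the outcome analysed (GAD-7, EQ-5D-5L or SF-12). Put the same list in the SAP, which has none.

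Remove imbalance as the selector in both sentences of section 8.5.2 and describe any observed imbalance without letting it change the model. If an imbalance-adjusted model is kept, label it a sensitivity analysis and state the candidate factors and the criterion.

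The cost is two sentences. Every covariate is already collected at baseline, so no new data and no change to the sample size are needed.

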8.2.5.2 Secondary Outcomes

There will be several secondary outcome measures to assess Wysa's ability to improve anxiety severity and identify people who need urgent support, engagement, and the acceptability and cost-effectiveness of the app (see Table 6). The secondary outcomes will also be measured at baseline and 3 months post randomisation.

Anxiety severity

As the GAD-7 [37], which measures anxiety symptoms, is recommended for the 6 most common presentations, it will also be used as an outcome measure for the study and will be presented to patients through the app in the same way as the PHQ-9 [36]. The remaining measures used by IAPT

are linked to specialist presentations of pre-existing conditions which would be excluded as participants from the study due to non-eligibility to IAPT standard pathway.

Crisis identification

Wysa's ability to identify users who are at high risk of a crisis and who need to be provided with additional support will be measured by comparing the number of patients that Wysa flags for escalation with the number of patients in the control group who contact the NHS Trust's crisis helpline or attend A&E. This data will be collected from iaptus, a cloud-based electronic patient record for managing psychological therapy services [38], which flags patients on the waitlist who access these crisis services.

Engagement

User engagement with Wysa will be assessed using a combination of complementary measures. Examining time spent using a digital health intervention is not by itself a reliable measure of effective engagement, as it cannot differentiate between users who spend a long time on the app because they're positively engaged compared to those who are frustrated and struggling to use it [39]. Therefore, objective measures of app usage will be supplemented with an assessment of uptake and dropout rates and a qualitative exploration of subjective user experience and engagement behaviour.

Acceptability

Wysa's acceptability will be examined through qualitative semi-structured interviews in a subset of participants. These interviews will provide a means of collecting in-depth data about participants' experiences with Wysa, what they liked and disliked, and why.

Health-related quality of life

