8.4.1.2 Allocation Concealment Mechanism

Consenting participants will be inputted into a masked computer randomisation algorithm and the outcome will be recorded in an electronic record to conceal treatment allocation from study researchers. Participants will be sent an automatic email to inform them of their group assignment, and participants in the intervention group will receive the link to download Wysa.

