8.4.3.1 Quantitative data collection

The quantitative outcome measures will be delivered directly to patients through the Wysa app or by Qualtrics survey (e.g. for participants in the control group). Participants in both conditions will complete four questionnaires at baseline and 3-months post-randomisation (PHQ-9, GAD-7, EQ-5D-5L, and SF-12). Outcome measures have been chosen that will not be a significant burden for participants to complete; none of the questionnaires are longer than 12 items or expected to take more than a few minutes each to complete. Together, the questionnaires should take participants from 10 to 20 minutes to complete. Patient responses will be automatically uploaded to the iaptus electronic patient records using the Mayden Prism API. App use data will be automatically stored through the app.

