13.4 Appendix 4. GP Letter

[header: GP letter Participant Consented, v1.0, XX/XX/XXXX; study logo]

[GP Name]

[GP Practice]

[Address]

[Date]

[Study Address]

[Address]

[Telephone/Email/Social media]

Our ref: XXXX

Dear Dr [GP name]

Re: [participant's full name], [participant's date of birth], [participant's address]

We would like to inform you that [participant's full name] has consented to join the Wysa Study. This project is a collaboration between the University of Plymouth, the Institute for Cancer Research, Wysa Ltd, and the Central North West London NHS Foundation Trust. The project is funded by the NIHR AI in Health and Care Award (ref: AI_AWARD02176) and has full ethical approval from [Research Ethics Committee (ref: TBD)]. No action is needed on your part, but [participant's full name] has provided permission that should anything of concern arise as a result of their participation in our study, we will discuss this with you.

Our study aims to measure and characterise the impact of engaging with Wysa while waiting for their first appointment through the IAPT service on symptoms of depression and anxiety. Participants randomised into the intervention group will be invited to use the app while waiting for treatment; participants randomised into the control group will be given access to the app after 3 months.

Participation is voluntary – [participant's name] is free to withdraw from our study at any point. If you would like any further information or if there is anything you would like to discuss, then please do not hesitate to contact us.

Yours sincerely,

[CI's/PI's name] Team Member's name]

13.5 Appendix 5. SPIRIT-AI Checklist: Recommended items to address in a protocol and related documents for clinical trials evaluating AI interventions

Section		SPIRIT 2013 Item ^a	SPIRIT-AI Item		Section No
Administrative Information					
Title	1	Descriptive title identifying the study design, population, interventions, and, if applicable, trial acronym	SPIRIT-AI 1(i) Elaboration	Indicate that the intervention involves artificial intelligence / machine learning and specify the type of model.	1
			SPIRIT-AI 1(ii) Elaboration	Specify the intended use of the AI intervention.	1

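### App dose arises after randomisation and only in the intervention arm, so it cannot serve as an effect modifier beside age and depression severity; any dose analysis here is a non-randomised comparison and should be labelled as such.

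*Protocol*

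**What the plan says.** Protocol 8.5.2 lists "pre-planned exploratory analyses for differential effects of the intervention for different age groups, depression severity, and interaction (dose) of the Wysa app" among the secondary analyses. A following sentence says that subgroup analyses for "differential effects in a priori specified groups will be conducted using linear or logistic regression". For secondary analyses that the study was not powered for, "we will report p-values but will focus on interpretation of 95% CI around estimates".

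Other sections fix where dose comes from and when:

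- Protocol 8.4.1.2: after allocation, "participants in the intervention group will receive the link to download Wysa".
- Protocol 8.4.3.1: "App use data will be automatically stored through the app".
- Protocol Appendix 4 (GP letter): "participants randomised into the control group will be given access to the app after 3 months". Protocol 8.2.5.1 places the primary outcome at the same 3 months.
- Protocol 8.4.1.1: age and severity of depression are balancing variables in the randomisation, so both are known before allocation.

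Neither document defines dose, names the comparison group for it, gives a causal method, or says that the comparison is not randomised. Protocol 8.6 (Limitations) does not mention it. The SAP's statistical methods cover arm comparisons of PHQ-9 and GAD-7 and post hoc regressions in baseline PHQ2 groups; dose does not appear.

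**The concern.** A differential-effect analysis asks whether the randomised contrast differs between groups that exist in both arms. Age group and depression severity allow that. Dose does not, because controls have no recorded dose against which the contrast could be formed.

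Dose also plausibly follows prognosis, and the Protocol's own description suggests that it could do so in either direction. Under section 6, a crisis trigger brings up grounding exercises and a stepped plan, so deterioration can itself generate use. Section 7.2.2 expects that some users will find the app sufficient, so improvement may change use. Section 8.2.5.2 accepts that "Examining time spent using a digital health intervention is not by itself a reliable measure of effective engagement", because long use may mean either engagement or struggle. Outcomes may also be collected through the app (8.4.3.1), so light users may be missing more often, which would add selection.

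At stake is the reading of a usage gradient. An inert app could show benefit rising with use, and a helpful app could look harmful if people who are getting worse use it more.

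**Working it through.** **Inputs.** From Protocol 8.3.2.1: 2-point PHQ-9 target, SD 6.6 (preliminary work 6.66), 80% power, N = 393 raised to 480 for 20% attrition, and 2:1 usual care to intervention. From Protocol 8.5.1: two-sided 0.05. From the SAP (Randomisation – implementation): 2:1 towards intervention. The two ratios conflict, so both are carried. Assumption: a residual correlation r between dose and 3-month outcome that is due to prognosis alone, from 0 to 0.3.

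**1. The plan's own figure.** Smaller arm n = (1 + 1/2) × [SD × (1.960 + 0.842)/2]².

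- SD 6.6: 128.2, so 129 + 258 = 387.
- SD 6.66: 130.6, so 131 + 262 = 393.

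The stated 393 reproduces exactly with the preliminary SD and within 2% with 6.6.

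**2. Intervention completers.** 480 × 0.8 = 384. One third is 128 (Protocol ratio); two thirds is 256 (SAP ratio).

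**3. What a dose model can estimate.** Write outcome = a + b·arm + c·dose + d·(arm × dose). In controls dose is 0, so the dose and arm × dose columns are identical. Only their sum c + d is estimable, and that is the slope among intervention users. No cross-arm interaction can be recovered.

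**4. False dose slope with an inert app.** P = Φ(m − 1.96) + Φ(−m − 1.96), with m = atanh(r) × √(n − 3). At r = 0.2:

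- n = 128: m = 0.2027 × 11.18 = 2.27, so P = 0.62.
- n = 256: m = 0.2027 × 15.91 = 3.22, so P = 0.90.

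| r | 128 completers | 256 completers |
|---|---|---|
| 0 | 5% | 5% |
| 0.1 | 20% | 36% |
| 0.2 | 62% | 90% |
| 0.3 | 93% | 99.8% |

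A negative r of the same size gives the same rates with the slope reversed.

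**5. Size of the apparent effect.** Heavier half minus lighter half = 2√(2/π) × r × SD = 1.596 × r × 6.6. This gives 1.05, 2.11 and 3.16 points at r = 0.1, 0.2 and 0.3. Heavier half against all controls is half of that: 0.53, 1.05 and 1.58. These use the unadjusted SD. If the adjustment covariates correlated 0.5 with outcome (an assumption), the SD would be 6.6 × √(1 − 0.25) = 5.72, and the 2.11 would fall to 1.596 × 0.2 × 5.72 = 1.83.

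**6. Simulation check** (4,000 inert-app trials per setting). The within-arm slope rates agree with step 4. At r = 0.1, 0.2 and 0.3, the top dose third against all controls is significant in 10%, 27% and 51% (128 users) or 12%, 34% and 66% (256 users). The comparison by randomised arm stays between 4.5% and 5.4% at every r.

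**The case against.** The case for leaving this alone has several parts.

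- **It is exploratory.** The text says so, states that the study was not powered for such analyses, and puts weight on intervals; the comparative analyses are intention to treat (8.5.1). This stands as a limit on consequence. It does not touch the bias.
- **It may not be live.** The SAP is later, mostly in the past tense, and has no dose analysis. Nothing shows that one was run. Equally, nothing withdraws it, so it could still be reported as pre-planned.
- **The model is partly inferred.** The regression sentence concerns groups specified in advance, and dose is not clearly one. A reader might infer that the plan writes down a dose-by-arm term; it does not. What is on the page is dose in the differential-effects list, without definition or comparator. Step 3 shows that no cross-arm version is available whichever model was meant.
- **The rates rest on an assumed correlation.** True. At r = 0 the error rate is nominal, so the figures show sensitivity and are not a forecast.
- **Controls might obtain the app themselves**, since Protocol 8.2.2 says that it is available on ordinary smartphones. Such use is neither planned for nor recorded as trial dose, so it gives no usable control dose.
- **The engagement passage concerns measurement, and not confounding.** Fair. It goes on to supplement usage with uptake, dropout and interviews. It is cited here only because it accepts that heavy use has opposite explanations.

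**Conclusion.** The point holds in a limited form. Dose cannot be an effect modifier across arms in this design, and a usage analysis that follows the 8.5.2 list would be a non-randomised comparison presented alongside valid baseline subgroups. At an assumed residual correlation of 0.2, an inert app gives a significant within-arm slope in about 62% to 90% of trials, depending on which document's allocation ratio applies. The unadjusted gap between halves is then about 2.1 points, close to the 2-point target, and smaller after covariate adjustment. The correlation, its sign and the normal model for usage are all assumptions.

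A reader might infer that a dose-response would be used to establish that the app works, because Protocol 10.1 says that the trial's data will support regulatory approval and adoption. The documents do not support that: 10.1 speaks of the data in general, and nothing ties the dose analysis to it. The primary comparison by randomised arm is unaffected.

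**What to change.** In Protocol 8.5.2, remove the dose item from the differential-effects list and keep only factors fixed at baseline. Add a separate sentence that associations between usage and outcome will be reported within the intervention arm, as descriptive and non-causal, with non-users counted as zero dose. The edit belongs in the Protocol, since the SAP has no dose wording to change. It costs a few words and needs no new data; the loss is that no dose-response claim can be made.

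Optional: if an effect of exposure is wanted, add a complier-average estimate with randomised arm as the instrument and one stated exposure definition. Three statements must go with it:

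- It relies on the exclusion restriction, that is, allocation affects outcome only through the exposure. This is open to question because participants and clinical teams are unblinded (8.4.2) and outcomes may come by app in one arm and Qualtrics in the other (8.4.3.1).
- It rescales the intention-to-treat effect and is not a dose-response.
- It is post hoc if the exposure is defined after unblinding.

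That adds one model on logged data, with an assumption that the data cannot verify.

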Real World Testing of an Artificial Intelligence-enabled App as an Early Intervention and
Support Tool in the Mental Health Referral Care Pathway

NCT05533190

8 August 2023

Methods

Randomisation – sequence generation

Demographic data was collected from all patients immediately after completion of the informed consent process, over the phone. Together with data from the IAPT referral, this information was used in the randomisation algorithm to ensure that the intervention and control arms were balanced on key variables (gender, age, ethnicity, self-reported antidepressant use, and severity of depression).

Randomisation – allocation concealment mechanism

Consenting participants were inputted into a masked computer randomisation algorithm and the outcome was recorded in an electronic record to conceal treatment allocation from study researchers. Participants were sent an automatic email to inform them of their group assignment, and participants in the intervention arm will receive the link to download Wysa.

Randomisation – implementation

Psychology assistants recruited specifically for the trial and covering the three London Community Living Well Service sites enrolled participants in the study. A computer generated the random allocation sequence assigned participants to interventions, with a ration of 2:1 randomization to the intervention group.

Blinding

Due to the nature of the intervention, no blinding of participants was possible in the study, as all participants knew whether they were using the app. Clinical treatment teams were not blinded as they knew through the electronic patient record if a participant has received the intervention. The evaluation team will be blinded to treatment using the randomisation algorithm.

Statistical methods

Descriptive statistics was used to assess baseline comparability and the distributions of the primary and secondary outcomes. Visualisations via density and box plots supplemented the tabulations. Linear regression was used to carry out comparative analysis of the primary outcome PHQ9, and secondary outcome GAD7, to compare the two treatment arms. For the primary outcome, PHQ9, the study was powered to detect a clinical meaningful difference of 2 points, with 80% power and a Type 1 error rate of 0.05. Additional post hoc regression was carried out for individuals who had a PHQ2<5 and PHQ2<4 at baseline.

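### Protocol 8.5.2 says its age and severity subgroups are specified in advance, but no band is given; a continuous interaction would lose less power and leave no cut-point to choose

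*Protocol*

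**What the plan says.** Protocol 8.5.2 plans exploratory analyses of "differential effects of the intervention for different age groups, depression severity, and interaction (dose) of the Wysa app". Its next sentence gives the method: "pre-planned exploratory subgroup analyses for differential effects in a priori specified groups will be conducted using linear or logistic regression". For secondary analyses that the study was not powered for, it adds that "we will report p-values but will focus on interpretation of 95% CI around estimates".

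No age band, PHQ-9 band, cut-point, reference category or form of interaction term follows. Protocol 8.3.2.1 and 8.4.1.1 and the SAP's randomisation text list age and depression severity as variables for adjustment or balance, also without categories, so no bands can be borrowed from the randomisation.

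The SAP's comparative analysis is described in one sentence: "Linear regression was used to carry out comparative analysis of the primary outcome PHQ9, and secondary outcome GAD7, to compare the two treatment arms". It does not mention the planned age or severity analyses. Its only baseline cut-points are in a different analysis, which it labels openly: "Additional post hoc regression was carried out for individuals who had a PHQ2<5 and PHQ2<4 at baseline". The protocol does not name PHQ2 as a measure.

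**The concern.** Two things are at stake.

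The first is the label. Calling groups specified in advance tells a reader that nobody could choose the boundaries after seeing results. That assurance needs the boundaries on record, and they are not in either document.

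The second is the method. Age and baseline PHQ-9 can enter a regression as numbers. Cutting them into groups treats everyone within a band as alike, which lowers the chance of seeing a real gradient in the treatment effect. It also creates a choice, where to cut, that a continuous term does not need.

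**Working it through.** **Inputs.** Protocol 8.3.2.1 gives the design values: "Based on a SD of 6.6 and a 2:1 recruitment ratio (usual care: intervention) a sample size of 393", for a 2-point difference with 80% power, and 480 recruited to allow 20% attrition. Protocol 8.5.1 gives a two-sided 0.05. Protocol 8.3.1 admits adults with no upper age limit and excludes PHQ-9 above 15. The documents give no figure for any subgroup or interaction analysis. The moderator distributions and the numbers of cut-points below are therefore assumptions. The protocol and SAP differ on which arm receives the larger share, but the figures here are the same either way.

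**The plan's own figure.** Larger arm = 3 × [SD × (1.960 + 0.842) / 2]².
- SD 6.6: 3 × 9.245² = 256.4, so 257 + 129 = 386.
- SD 6.66 (the preliminary SD in 8.3.2.1): 3 × 9.329² = 261.1, so 262 + 131 = 393, as stated.
- 480 × 0.8 = 384 completers (256 and 128), used from here on.

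**Continuous interaction.** For a moderator in SD units, the standard error of the arm-by-moderator slope is 6.6 / √(384 × 2/9) = 6.6 / 9.238 = 0.714. Power is approximately Φ(slope / 0.714 − 1.960).

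**Median split.** For a normal moderator a median split keeps 2/π = 63.7% of the information, so slope / SE is multiplied by √0.637 = 0.798. Equal power would need 1 / 0.637 = 1.57 times the sample.

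| Slope (points per SD) | Continuous | Median split |
|---|---|---|
| 2.0 | Φ(2.80 − 1.96) = 80% | Φ(2.24 − 1.96) = 61% |
| 1.0 | Φ(1.40 − 1.96) = 29% | Φ(1.12 − 1.96) = 20% |
| 0.5 | about 11% | about 9% |

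Uneven splits lose more: at the slope of 2.0, a 30/70 split has 57% power and a 20/80 split 50%.

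**Other distributions, by simulation** (384 completers, 2:1, SD 6.6, slope about 2 points per SD, continuous test 78-80%):
- Age median split: 60% if age is normal, 65% if uniform, 55-56% if right-skewed.
- Three equal age groups: 59%, 64% and 55% respectively.
- An integer PHQ-9 truncated at 15 and cut at 10: 64%, against 79% continuous.

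**False positives with no true interaction, by simulation:**
- Continuous term: 4.7-5.0%.
- One median cut fixed in advance: 5.5%, compatible with the nominal 5%.
- Best of two age cuts (30, 50): 9.4-9.5%. Best of four (30, 40, 50, 60): 15.3-15.6%. Best of eight (25 to 60 in fives): 23.1%.
- Best of three quartile cuts: 12.8%. Best of nine decile cuts: 24.9%.
- PHQ-9 truncated at 15: 9.9% for two cuts, 16.5% for four.

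**The case against.** The plan is candid about the status of these analyses: exploratory, not specifically powered, and read mainly through confidence intervals. Grouped displays are conventional, and one set of bands fixed in advance would make the label true and hold each test at 5%. This stands. It limits the importance of the point, although p-values are still promised and a fixed cut still loses power.

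A reader might infer that the error rate is inflated. The documents do not support that. Inflation requires several cuts to be tried and the best kept, and nothing in either document says this was planned or done. Bands chosen without sight of outcomes keep 5%.

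A reader might also infer that severity is certain to be grouped. Protocol 8.5.2 attaches the word groups to age, and lists severity without it. The following sentence on subgroup analyses makes grouping of severity likely, but a regression with continuous severity remains open.

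The 80% versus 61% contrast is drawn at a very large interaction: 2 points per SD equals the trial's whole target difference for each SD of the moderator. At smaller slopes both versions are underpowered and the absolute gain shrinks. This too stands.

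Finally, the SAP's PHQ2 subsets might be read as the missing bands presented as planned. They are labelled post hoc and are not evidence of mislabelling.

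**Conclusion.** The point holds in a limited form. The groups are described as set in advance and neither document sets them, so the description is unsupported. Age is to be grouped, and severity possibly so. Under a linear interaction, 384 completers, 2:1 allocation and SD 6.6, a median split has about 55-65% power where the continuous test has about 80%, and about 20% against 29% at half that slope. The false-positive range of roughly 9-25% is conditional on searching an assumed 2 to 9 cut-points. It describes what undefined bands would permit and is not a finding about this trial.

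The consequences are confined to exploratory analyses; the primary comparison is untouched. That age is held as a number is also an assumption, though a likely one: protocol 8.4.1.1 says only "Demographic data will be collected from all patients immediately after they complete the informed consent process".

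**What to change.** In protocol 8.5.2 and the SAP, define the moderator analysis as one arm-by-age and one arm-by-baseline-PHQ-9 interaction, each with the moderator continuous. Report the estimated treatment effect with its 95% CI at a few fixed values of the moderator, such as the quartiles. Add a restricted cubic spline as a limited check of linearity. Keep any table by age or severity band as description, with the bands stated.

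The SAP, dated 8 August 2023, describes its analyses largely in the past tense and contains no age or severity moderator analysis. An interaction added now could not itself be called specified in advance. If neither the bands nor the form of the interaction were documented before the data were seen, label the analysis post hoc.

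The cost is wording and a short analysis within the regression already planned, with no new data provided age was recorded as a number. The downside is a linearity assumption that the spline can check only weakly at this sample size. Two such tests, if independent, still carry a joint false-positive rate of 1 − 0.95² = 9.75%, so the emphasis on intervals should stay.
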